#### 1.1. Trial Design

This study consisted of a double-blind, randomised, controlled, unicentric trial with two parallel arms depending on the cooked meat product consumed (control and reformulated), with a duration of 5 weeks. The study was approved, according to the Declaration of Helsinki, by the Bioethics Committee of the University of Murcia (UMU) with code 550/2023. The research took place at the Department of Nutrition and Bromatology of the Faculty of Veterinary Medicine of the University of Murcia. Investigators provided a detailed explanation of the protocol to participants, and those choosing to participate gave their informed consent. Each participant received a unique code based on their arrival order. Following this, an external researcher then assigned the participants to the different groups with the aim of having two similar groups based on sex, age, and IMC. The specific group assignments were not known to either the researchers or the participants.

Three weeks before the start of the study, a recruitment phase was carried out, in which potential participants were recruited and informed about the details of the study. From a total of 63 individuals initially recruited, fifty-eight volunteers completed the trial. Participants who abandoned the trial were for personal reasons unrelated to the study. Two visits were made during the experimental phase of the intervention: the initial and the final visit. At both visits, blood, faeces, and urine samples were obtained from participants, and anthropometric measurements were also taken. Two deliveries of 15 blister packs of 100g control or reformulated cooked meat product were made, at baseline and after 17 days. Individuals consumed one blister pack per day for 6 days per week. Throughout the trial, subjects recorded their complete diet in a collection notebook, which was given to the researchers at the end of the study.

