#### 1.2. Participants

The study comprised a total of 58 subjects divided into two groups of 29 individuals with similar characteristics (Table 2). To participate in the study, subjects were required to be between 18 and 65 years of age and body mass index (BMI) between 18.5 and 30 kg/m2. Participants also had to avoid all of the exclusion criteria: use of antibiotics in the last 3 months; use of medication for hypertension or for the treatment of hyperlipaemia; consumption of pre- or probiotic supplements; consumption of omega-3 or omega-6 supplements; eating , intestinal or similar problems; diabetes mellitus, chronic kidney disease, liver disease, infectious diseases or any type of cancer; having donated blood in the last month; having undergone surgery within the last three months; abusive alcohol consumption; being vegetarian; being pregnant; being a smoker; and participation in other clinical trials in the last 3 months.

		0 1	
	Control	Intervention	p-value 
Age (years)	$26.6 \pm 11.5$	$26.7 \pm 11.7$	0.97
Men	15	14	1.00
Women	14	15	1.00
BMI (kg/m2)	$23.7\pm2.7$	$23.6\pm2.8$	0.98
Weight (kg)	$66.6 \pm 11.8$	$68.4 \pm 12.7$	0.58
Fat mass (%)	$26.0\pm9.0$	$26.9\pm9.0$	0.71
Total colesterol (mg/dl)	$175.8 \pm 34.6$	$178.0 \pm 30.9$	0.80
Oxidized LDL (ng/mL)	$238.6 \pm 52.1$	$233.6 \pm 52.4$	0.71

Table 1. Distribution of volunteer demographics
---

 $^1$  p-values between control and intervention groups were examined using a one-way analysis of variance (Tukey's test). The results are shown as mean  $\pm$  SD (n=29).

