#### 1.4. Statistical analysis

Data analysed were expressed as mean  $\pm$  standard deviation (SD). Student's t-test was used to analyse significant differences over time (baseline and final). To analyse the differences between groups in the evolution of the different variables, an analysis of variance (ANOVA) was performed for repeated measures, with time (baseline and final) as the within-subject factor, and the product consumed (Control and Intervention) as the between-subject factor. Tukey's test was carried out for post hoc analysis. Cross-tabulation and chi-square tests were conducted to determine the perception of respondents on food additives based on demographic data.

Data processing and statistical analysis were performed using SPSS version 28.0 (IMB Corp., Armonk, NY, USA) with a significant level of  $p \le 0.05$ .

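### The protocol calls the trial randomised, but the only allocation step it describes contains no element of chance

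*Protocol*

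**What the plan says.** Section 1.1 of the protocol (Trial Design) opens with the label: "This study consisted of a double-blind, randomised, controlled, unicentric trial with two parallel arms". The same paragraph then describes how people reached their arm, in this order:

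- After consent, "Each participant received a unique code based on their arrival order".
- Next, "an external researcher then assigned the participants to the different groups with the aim of having two similar groups based on sex, age, and IMC". I read IMC as body mass index.
- On blinding, "The specific group assignments were not known to either the researchers or the participants".

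On numbers, section 1.1 says "From a total of 63 individuals initially recruited, fifty-eight volunteers completed the trial", and section 1.2 (Participants) describes "58 subjects divided into two groups of 29 individuals with similar characteristics". Section 1.4 (Statistical analysis) compares the arms by repeated-measures ANOVA with "the product consumed (Control and Intervention) as the between-subject factor" and names no covariates.

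**The concern.** The label and the procedure do not match. The procedure names the person who assigned and the aim of the assignment, and nothing else. Someone following it literally could place each participant by judgement, knowing sex, age and BMI, and would be fully compliant without any use of chance.

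This is more than a detail that a statistical analysis plan could supply. Allocation is part of the design. The protocol does describe a procedure, and that procedure lacks the property claimed for it. An analysis plan cannot make judgement-based placement random afterwards.

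What is at stake is how a time-by-product difference may be read. Deliberate balancing protects the factors that are balanced. Random assignment is what gives protection, in expectation, for everything else. Here that includes habitual diet and baseline microbiota, which bear directly on the short-chain fatty acid, 16S sequencing and urinary nitrate and nitrite measurements in sections 1.3.3 and 1.3.4. The protocol makes no causal claim in words, but a randomised controlled label together with a between-product test implies one.

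**Working it through.** The protocol gives no planning figure on this point, so there is none to reproduce. The check has two parts.

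**1. The text.** In the whole protocol, randomisation is mentioned once, as the label in section 1.1. The features that would show a chance element are:

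| Feature | Stated in the protocol? |
|---|---|
| Random sequence or how it was generated | No |
| Blocks or strata | No |
| Minimisation with a random component | No |
| Who held the list, and concealment before assignment | No |
| Assigner external to the team | Yes (1.1) |
| Assignments unknown to researchers and participants | Yes (1.1) |
| Balancing aim on sex, age and BMI | Yes (1.1) |

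The items that are stated concern who assigned, the balance aimed for and who was kept blind. None of them is a source of chance.

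**2. What Table 1 (section 1.2) can and cannot show.** Inputs are the printed means and SDs, with n = 29 per arm. The formula is t = d / √[(s₁² + s₂²)/29] on 56 degrees of freedom, which for two groups is equivalent to one-way ANOVA. The standardised difference is d / √[(s₁² + s₂²)/2].

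- Age: d = 0.1, SE = √[(11.5² + 11.7²)/29] = 3.05, t = 0.033, p = 0.974 (printed 0.97).
- BMI: d = 0.1, SE = √[(2.7² + 2.8²)/29] = 0.722, t = 0.138, p = 0.89 (printed 0.98). Rounding of the means allows 0.78 to 1.00, so the printed value is compatible.

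| Variable | Printed p | Recomputed p | Standardised difference |
|---|---|---|---|
| Age | 0.97 | 0.974 | 0.009 |
| BMI | 0.98 | 0.89 | 0.036 |
| Weight | 0.58 | 0.578 | 0.147 |
| Fat mass | 0.71 | 0.705 | 0.100 |
| Total cholesterol | 0.80 | 0.799 | 0.067 |
| Oxidised LDL | 0.71 | 0.717 (0.712 to 0.722 with rounding) | 0.096 |

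Sex is split 15/14 against 14/15, which is as even as 29 men and 29 women in two groups of 29 can be. The Fisher p-value is 1.00. An unrestricted random split would be this even with probability 2·C(29,14)·C(29,15)/C(58,29) = 0.40, so sex alone tells us little.

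Age and BMI, two of the factors named in the balancing aim, have the smallest standardised differences. That agrees with the stated aim. Stratified randomisation, minimisation with a random component and placement by hand would all produce this pattern.

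The equal arms do not help either. Suppose the 63 recruits had been split 32/31 (an assumption, since the protocol does not give the split) and the 5 losses fell at random. The chance of ending at exactly 29/29 is C(32,3)·C(31,2)/C(63,5) = 4,960 × 465 / 7,028,847 = 0.33.

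**The case against.** The strongest reply is that the text is silent on method, and silence does not establish a non-random design. Similar groups on sex, age and BMI are also the aim of stratified randomisation and of minimisation, and the same paragraph calls the trial randomised. This stands. A reader might infer that allocation was shown to be purposive matching, but the protocol does not support that. It shows only that the stated procedure lacks a chance element.

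A reader might also take the very close balance on age and BMI as evidence against randomisation, by working out how rarely simple randomisation would produce it. That comparison is not informative. The protocol openly says the groups were balanced, so simple randomisation is the wrong reference, and the BMI p-value is uncertain between 0.78 and 1.00 from the printed figures.

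A third tempting inference is that the p-values of section 1.4 become invalid. That goes too far. The repeated-measures ANOVA rests on model assumptions, and its time-by-product term compares changes, so stable differences in level between people cancel. Selection related to change remains possible, but nothing in the protocol demonstrates it.

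The safeguards also count. Consent and coding are described before assignment, the assigner was external, and the assignments were hidden from researchers and participants. Nothing says that the assigner saw diet, lipids or microbiota. These features limit performance and detection bias and narrow the route for deliberate selection. They do not replace a random sequence, and Table 1 says nothing about diet or microbiota.

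**Conclusion.** The point holds in a limited form. The protocol claims randomisation, and its stated allocation procedure does not provide it. Whether an unstated random step was used cannot be decided from the document.

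No amount of bias can be calculated. In Table 1 the largest standardised difference is 0.15 (weight), and the two lipid measures shown differ by less than 0.10, so no imbalance is visible among the variables reported. That table covers 58 completers of 63 recruited (5/63 = 7.9% lost), so balance at allocation cannot be checked.

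The conclusion rests on the text of section 1.1 and on the absence of any chance mechanism elsewhere in the protocol. It does not rest on the baseline p-values. It needs correcting because it concerns the central design label and how far a between-product difference may be attributed to the product.

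**What to change.** Replace the allocation sentence in section 1.1 with what was actually done:

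- **If there was a random element:** name the mechanism, for example minimisation on sex, age and BMI with a random component, or a permuted-block list stratified on those factors. Say who generated and held it, and account for those factors in the between-group analysis of section 1.4.
- **If there was none:** delete the randomised label and describe a blinded controlled trial with balanced non-random allocation. Adjust the product comparison for sex, age, BMI and the baseline value, and word the conclusions accordingly.

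The protocol is written in the past tense and reports completers, so a new allocation script would apply only to anyone not yet allocated. A mechanism that was not used must not be written in afterwards.

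The cost is one rewritten sentence, a model statement and, in the second case, a less favourable design label. With one parameter for each of the four covariates, an adjusted comparison of final values keeps 58 − 2 − 4 = 52 residual degrees of freedom. No extra participants or procedures are needed.

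### Allocation aimed to balance sex, age and BMI, but the between-group model in 1.4 contains only time and product: a minor loss of precision, cheap to recover, if these factors predict change

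*Protocol*

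**What the plan says.** Section 1.1 describes a "double-blind, randomised, controlled, unicentric trial with two parallel arms". It then says that an external researcher "assigned the participants to the different groups with the aim of having two similar groups based on sex, age, and IMC". It gives no further detail of how assignments were generated. It also reports that "fifty-eight volunteers completed the trial", out of 63 recruited.

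Section 1.2 describes "two groups of 29 individuals with similar characteristics". The baseline table shows age 26.6 ± 11.5 v 26.7 ± 11.7 years, men/women 15/14 v 14/15, and BMI 23.7 ± 2.7 v 23.6 ± 2.8 kg/m² (control v intervention).

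Section 1.4 sets the between-group analysis. "To analyse the differences between groups in the evolution of the different variables", it uses a repeated-measures ANOVA "with time (baseline and final) as the within-subject factor" and "the product consumed (Control and Intervention) as the between-subject factor". No covariate is named.

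**The concern.** The design used three factors and the stated model uses none of them. When allocation forces balance on a factor that predicts the outcome, that factor's contribution is largely removed from the difference between groups. If the factor is left out of the model, its contribution stays in the error term. The standard error is then larger than the real uncertainty of the estimate.

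What is at stake is efficiency: somewhat wide intervals and somewhat less power from the same 58 people. Only prediction of *change* matters here. A stable effect of sex, age or BMI on the *level* of an outcome cancels within each participant.

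**Working it through.** The protocol gives no sample size calculation, effect size, SD of change or R², so there is no design figure to reproduce.

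**Inputs from the protocol.** 29 per arm; Table 1 means, SDs and counts; significance level 0.05 (taken as two-sided).

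**Assumptions.** R², the share of variance in change explained by sex, age and BMI, from 0 to 0.1. Correlation ρ between baseline and final values. A true effect set to give 80% power unadjusted.

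**1. Balance achieved (completers only).**
- Age: 0.1/11.6 = 0.009 SD.
- BMI: 0.1/2.75 = 0.036 SD, from the rounded means.
- Sex: (1/29)/0.509 = 0.068 SD.
- Sum of squares D² ≈ 0.0060. The variance of the adjusted product effect is inflated by 1 + 14.5 × 0.0060/56 = 1.0016, where 14.5 = 29 × 29/58. Adjustment therefore costs almost nothing through imbalance.
- If the three factors share R² = 0.1 equally and all act in the same direction, residual imbalance shifts the unadjusted estimate by √(0.1/3) × (0.009 + 0.036 + 0.068) = 0.021 SD.

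**2. The test in 1.4.** With two time points, time-by-product is a two-sample t-test on change with 58 − 2 = 56 df. Power is 80% when 0.749 × √14.5 = 2.85 is the noncentrality, so the reference effect is 0.749 SD of change.

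**3. Unadjusted against adjusted.** Given the balance, the group difference has variance (1 − R²) × 2/29, while the unadjusted error variance still averages 1 (in units of the variance of change). The adjusted model has 58 − 5 = 53 df and error variance 1 − R².

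| Assumed R² | 0 | 0.02 | 0.05 | 0.1 |
|---|---|---|---|---|
| Type I error, unadjusted (%) | 5.0 | 4.8 | 4.5 | 3.9 |
| Power, unadjusted (%) | 80.0 | 80.2 | 80.6 | 81.2 |
| Power, adjusted (%) | 79.9 | 80.6 | 81.8 | 83.8 |
| Difference (points) | −0.1 | 0.4 | 1.2 | 2.6 |
| Interval width, unadjusted/adjusted | 1.00 | 1.01 | 1.02 | 1.05 |

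A separate simulation, taking the best balanced of 100 random splits, gave the same pattern at R² = 0.1: type I error 3.8%, power 81.1% unadjusted and 83.9% adjusted.

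**4. In units.** For total cholesterol the pooled baseline SD is √((34.6² + 30.9²)/2) = 32.8 mg/dl. With ρ = 0.8 assumed, the SD of change is 32.8 × √(2 × 0.2) = 20.7 and the standard error is 20.7 × √(2/29) = 5.45. The 95% half-width is 2.003 × 5.45 = 10.9 mg/dl. Adjusted, it is 10.7 (R² = 0.05) or 10.4 (R² = 0.1).

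**5. ANCOVA on the baseline value.** Its residual variance relative to change is (1 − ρ²)/(2(1 − ρ)) = (1 + ρ)/2, with 58 − 6 = 52 df. Even at R² = 0, power is about 90 / 86 / 84 / 82% for ρ = 0.5 / 0.7 / 0.8 / 0.9. This gain comes from estimating the baseline slope, not from the three factors.

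**The case against.** **This is preference, not error.** Balanced allocation and an unadjusted ANOVA do not contradict each other, and many trials leave covariates to the SAP, which is not at hand. The first part stands: nothing here is inconsistent, and the point is about efficiency. The second carries less weight, because 1.4 itself specifies the model and both its factors. If a SAP already adds the covariates, 1.4 only needs to be aligned with it.

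**The size is assumed.** This stands. Nothing in the protocol shows that sex, age or BMI predicts 5-week change, and at R² = 0 adjustment is very slightly harmful. The gain may be negligible.

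**Conservatism depends on how allocation was done.** This also stands. In simulation with a simple random split, the unadjusted test kept its level (4.8 to 5.3%). The values below 5% in the table hold when a random procedure enforces the balance.

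**Stronger readings.** A reader might infer that assigning people to obtain similar groups means the trial was not randomised. The text does not support that: stratified randomisation and minimisation have the same aim, and 1.1 calls the trial randomised. Nor does the text show that a chance element was present, so the unadjusted test cannot be called valid without that condition. A reader might also infer that omitting the factors produces false positives or a material bias. With a random component the error runs the other way, and the imbalance in Table 1 is too small for more than about 0.02 SD at R² = 0.1.

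**Age is probably skewed.** A mean of 26.6 with SD 11.5 and a minimum of 18 implies a long right tail, so a linear age term may give a few older participants high leverage. This is fair and worth checking when the model is fitted.

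**Conclusion.** The point holds as a minor efficiency improvement. The model in 1.4 leaves out the three factors that allocation was meant to balance. If allocation had a random component, the between-group test is conservative to the extent that those factors predict change. Over an assumed R² of 0 to 0.1, this costs about 0 to 3 points of power and widens intervals by 0 to 5%. R², ρ and the reference effect are assumptions. Table 1 describes the 58 completers, not all 63 recruited. If allocation had no random component, the statement about conservatism does not apply, and covariate adjustment would not supply a randomisation basis.

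**What to change.** In 1.4, analyse the final value by ANCOVA on product, baseline value, sex, age and baseline BMI (52 error df). When BMI is the outcome, enter baseline BMI once (53 error df). This is preferred because it also takes the larger gain from the baseline value.

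If the repeated-measures ANOVA is kept, enter sex, age and baseline BMI each crossed with time (53 error df). A covariate main effect alone leaves the time-by-product test unchanged. The two models are not equivalent, so one should be chosen and named.

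The trial is reported as completed, so keep the analysis in 1.4 and report the adjusted model beside it, labelled post hoc or sensitivity unless it was fixed before the data were seen. Align it with any SAP. In 1.1, state how assignments were generated and what their random component was.

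**Cost.** No new data are needed. If the covariates predict nothing, the change model loses 3 df and 0.1 to 0.2 point of power. The ANCOVA loses 4 df and at most about 0.5 point; that worst case has ρ near 1 and the largest baseline difference in Table 1, weight, at 1.8/12.3 = 0.15 SD. The other cost is status: a post hoc adjusted result cannot replace the stated analysis, so the power gain then supports interpretation only.

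### The 58 completers (29 v 29) stand as the study population, and the number allocated per arm and the arm and timing of the five losses are not given, so the comparison is not shown to include everyone allocated

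*Protocol*

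**What the plan says.** Section 1.1 (Trial Design) gives the order as consent, a code by order of arrival, and then allocation: "an external researcher then assigned the participants to the different groups with the aim of having two similar groups based on sex, age, and IMC". A second paragraph describes recruitment, "Three weeks before the start of the study, a recruitment phase was carried out", and continues: "From a total of 63 individuals initially recruited, fifty-eight volunteers completed the trial". On the losses it says only this: "Participants who abandoned the trial were for personal reasons unrelated to the study".

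Section 1.2 (Participants) states: "The study comprised a total of 58 subjects divided into two groups of 29 individuals with similar characteristics". The demographics table there (captioned Table 1) is on n = 29 per arm.

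Section 1.4 (Statistical analysis) gives the between-group test: "an analysis of variance (ANOVA) was performed for repeated measures, with time (baseline and final) as the within-subject factor", with product as the between-subject factor. It names no analysis set and describes no imputation.

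No section gives the number allocated to each arm.

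**The concern.** The number that completed and the number the study is said to comprise are the same, 58. The baseline table uses that denominator, and the chosen test cannot use a person without a final value. Read together, these sections describe a comparison of completers.

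If any of the five had already been allocated, the comparison leaves out allocated people, and the balance created at allocation is no longer guaranteed. The similarity shown in Table 1 would then be similarity after the losses, which says nothing direct about the groups as allocated. A general statement that the reasons were personal gives neither arm nor timing, so a reader cannot tell a harmless loss from one that shifts the estimate.

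**Working it through.** **Inputs from the protocol.** Recruited 63 and completed 58 (section 1.1); 29 per arm (section 1.2); significance level 0.05 (section 1.4), taken here as two-sided. No sample-size or power figure is stated.

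**Reproducing the protocol's figures.**
- 29 + 29 = 58; by sex, 15 + 14 = 29 in each arm.
- 63 − 58 = 5 lost; 5/63 = 7.9%.
- Table 1 p-values, recomputed from the printed means and SDs at 29 per arm (stated value in brackets): age 0.97 (0.97), weight 0.58 (0.58), fat mass 0.71 (0.71), total cholesterol 0.80 (0.80), oxidised LDL 0.72 (0.71, within rounding), sex 1.00 (1.00). BMI gives 0.89 (0.98), but rounding of the means alone allows 0.78 to 1.00.

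The table is therefore consistent with its stated n = 29 per arm, that is, with the 58.

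**What the test requires.** With two visits, the time-by-product term of the repeated-measures ANOVA is equivalent to a two-sample test on the change from baseline. A person without a final value has no change and drops out unless a value is imputed.

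**Size of a possible bias.** Assumptions: all five left after allocation, and leavers' mean change differs from completers' by d SD of change, in the same direction and by the same amount in both arms. With a and b losses in the two arms (a + b = 5):

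shift = [a/(29 + a) − b/(29 + b)] × d

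SE of the difference in mean change = √(2/29) = 0.263 SD; 95% CI half-width ≈ 0.53 SD.

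true two-sided error = P(|Z + shift/SE| > 1.96)

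| Split | Allocated | Loss per arm | Shift, SD (d = 0.5 / 1.0 / 1.5) | True error (d = 0.5 / 1.0 / 1.5) |
|---|---|---|---|---|
| 3 v 2 | 32 / 31 | 9.4% v 6.5% | 0.01 / 0.03 / 0.04 | 5.0% / 5.1% / 5.3% |
| 4 v 1 | 33 / 30 | 12.1% v 3.3% | 0.04 / 0.09 / 0.13 | 5.3% / 6.3% / 7.9% |
| 5 v 0 | 34 / 29 | 14.7% v 0% | 0.07 / 0.15 / 0.22 | 5.9% / 8.7% / 13.4% |

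Example, 5 v 0 at d = 1: 5/34 = 0.147; 0.147/0.263 = 0.56; P(Z > 1.40) + P(Z < −2.52) = 0.087.

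If all five left before allocation, there is no loss after allocation and the shift is 0.

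**A limit of the table.** The protection from a 3 v 2 split depends on similar leavers in both arms. If leavers differed by 1 SD in opposite directions, the two terms would add: 3/32 + 2/31 = 0.094 + 0.065 = 0.158 SD. The protocol gives no sign of this, but it is why a sensitivity analysis should vary the shift by arm.

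**The case against.** **The five may never have been allocated.** The 63 are described only as recruited, directly after the recruitment phase, and no sentence says that 63 were allocated. This stands. The remark that people abandoned the trial leans towards their having entered it, but does not settle the matter.

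**A reader might infer that the comparison is not made by allocated group.** The protocol does not support that. Nothing suggests that any completer was analysed outside the assigned arm. The most that can be at issue is the exclusion of allocated people.

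**Analysis sets and missing-data rules may be in a statistical analysis plan that is not shown.** This stands in part: section 1.4 does not say that allocated people were dropped, and the test alone does not rule out imputation. The completers-only reading is therefore an inference. It is a strong one, because this document itself fixes the population at 58, the baseline denominator at 29 and a test that needs both visits.

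**The larger error figures rest on the least likely split.** Allocation aimed at two similar groups. That does not fix arm size, but 32 and 31 is the natural reading of 63 allocated, and reaching 29 v 29 from there needs a 3 v 2 loss, where the effect is negligible for similar leavers. This stands. The 8.7% and 13.4% figures are worst cases under assumptions, not estimates for this trial.

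**The losses are not hidden.** The total and a general reason are given. A reader might infer that the daily product drove people out; the protocol says the reasons were unrelated to the study, and nothing in it shows otherwise. Only arm and timing are missing.

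**A mixed model would not remove the bias.** Correct. Leavers could add at most a baseline value, and the model assumes that missing values are predictable from observed data. Its main benefit is precision.

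**Conclusion.** The point holds in a limited form: the protocol describes a comparison of 58 completers and does not show that this includes everyone allocated. A bias is possible but not demonstrated. With leavers who differ from completers alike in both arms, the shift runs from zero (all left before allocation), through 0.01 to 0.04 SD (3 v 2), to about 0.15 SD (all five from one arm, assumed 1 SD difference). Even 0.15 SD is well inside the 95% CI half-width of about 0.53 SD. The leaver differences are assumed throughout, because the protocol gives no data on those who left. The change is worth making because it is cheap, uses data already held, and lets a reader see which case applies.

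**What to change.** 1. State the number allocated to each arm, and the arm and timing of each of the five losses. If all five left before allocation, say so; the 58 are then the full set, and steps 2 and 4 have nothing to add.
2. Otherwise, define the main analysis set as all allocated participants in their assigned arm, and show Table 1 for that set. Keep the 58 completers as a secondary set.
3. Replace the repeated-measures ANOVA with a baseline-adjusted model: a mixed model with a common baseline mean, or ANCOVA on the final value. With equal variances at the two visits and baseline–final correlation ρ, the variance of the treatment difference is (1 + ρ)/2 times that of the change analysis, so precision improves whenever ρ is below 1. This step does not by itself deal with leavers who differ from completers.
4. Add one sensitivity analysis that imputes the missing final values over a range of shifts, set separately for each arm.

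Cost: wording changes and a little more analysis. No new participants or measurements are needed. The sensitivity intervals may be slightly wider.
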